During clinical development, the number of subjects 4 years of age and older with PGTCs exposed to levetiracetam was considerably smaller than the number with POS. As in the POS subjects, behavioral symptoms appeared to be associated with levetiracetam treatment. Gait disorders and somnolence were also described in the study in PGTCs, but with no difference between placebo and levetiracetam treatment groups and no appreciable discontinuations. Although it may be expected that drug-related events seen in POS subjects would be seen in PGTCs subjects (eg, somnolence and gait disturbance), these events may not have been observed because of the smaller sample size.²⁴

Discontinuation or Dosage Reduction in Well-Controlled Clinical Studies

The adverse events most commonly associated ($\geq 3\%$ in subjects receiving levetiracetam) with discontinuation or dosage reduction in the well-controlled pediatric POS study were asthenia, hostility, and somnolence. The adverse event most commonly associated ($\geq 3\%$ in subjects receiving levetiracetam) with discontinuation or dosage reduction in the well-controlled pediatric JME study was anxiety (2 subjects, 3.3%), but the small study size (a total of 113 subjects enrolled with JME) limits the conclusions that can be drawn. The PGTCs study was too small to adequately characterize the adverse events leading to discontinuation or dosage reduction.²⁴

Hematologic Abnormalities

Levetiracetam-treated pediatric subjects with POS experienced small, but statistically significant, decreases in white blood cell (WBC) and neutrophil counts and increases in lymphocyte counts, as compared with placebo. In a well-controlled study, more levetiracetam-treated pediatric subjects with POS had a possibly clinically significant abnormally low total WBC value (3.0%

levetiracetam-treated versus 0% placebo); however, there was no apparent difference between treatment groups with respect to neutrophil count. No subject was discontinued secondary to low WBC or neutrophil counts. Although there were no obvious hematologic abnormalities observed in subjects with JME, the limited number of subjects limits the conclusions that can be drawn.²⁴

Liver Function Test Abnormalities

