There were no meaningful changes in mean LFT values in controlled studies in adult or pediatric subjects; LFT abnormalities were similar in drug- and placebo-treated subjects in controlled studies (1.4%). No pediatric subjects were discontinued from controlled studies due to LFT abnormalities.²⁴

Impaired Renal Function

Levetiracetam is known to be substantially excreted by the kidney, and the risk of adverse reactions to this drug may be greater in patients with impaired renal function.²⁴

Post-Marketing Experience With Adjunctive Therapy

The following have been reported in patients receiving marketed levetiracetam worldwide (alphabetical order): abnormal LFT values, choreoathetosis, dyskinesia, erythema multiforme, hepatic failure, hepatitis, leukopenia, neutropenia, pancreatitis, pancytopenia (with bone marrow suppression identified in some of these cases), Stevens-Johnson syndrome, thrombocytopenia, toxic epidermal necrolysis, and weight loss. Alopecia has been reported with levetiracetam use; recovery was observed in the majority of cases where levetiracetam was discontinued.

Levetiracetam Monotherapy

Levetiracetam is not approved as monotherapy for epilepsy; however, investigator-initiated studies of children with epilepsy support its use in this indication. These monotherapy studies used the same titration and maintenance dosing as pivotal adjunctive studies; overall efficacy and safety outcomes were similar in both treatment settings.^{21,24,29,43}

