13. Subject has clinically relevant abnormalities noted on renal ultrasound or DEXA scans. Subjects with baseline BMD Z-scores ≤ -2 , for either posterior-anterior lumbar spine (L1-L4) or total body less head, will not be enrolled.
14. Subject has congenital glaucoma or known ocular deficits, or is receiving any ocular medications except lubricating eye drops or topical antibiotics.
15. Subject has a known history of central hyperthermia, dysautonomia, or other disturbances of autonomic function.
16. Subject has a known history of inborn errors of metabolism, mitochondrial dysfunction, or prior evidence of hyperammonemia.

-
17. Subject has any clinically significant abnormality in laboratory tests at screening, including but not limited to:
 - WBC count $<3,000/\mu\text{L}$ or absolute neutrophil count $<1,000/\mu\text{L}$ in the last 6 months
 - Aspartate aminotransferase (AST), alanine aminotransferase (ALT), or gamma-glutamyltransferase (GGT) ≥ 3 times the ULN
 - Total bilirubin ≥ 1.5 mg/dL or conjugated bilirubin $\geq 20\%$ of total
 - Venous ammonia ≥ 2 times the ULN
 - 25-hydroxy-vitamin D (level for clinically significant vitamin D deficiency is <12.0 ng/mL, conventional units [<30 nmol/L, SI units])^{19,42}
 - Parathyroid hormone (normal reference range is 14.0 to 72.0 pg/mL)
 - 1,25-dihydroxy-vitamin D, as determined by the age-dependent reference ranges (see lab manual)
 - Insulin-like growth factor 1 (IGF-1), as determined by the age-dependent reference ranges (see lab manual)
 18. Subject has a bicarbonate level <20 mEq/L, has a diagnosis of metabolic acidosis, or is on alkali therapy.
 19. Subject has refractory epilepsy and requires adjunctive AED therapy or is receiving >1 concurrent AED (including benzodiazepines, regardless of the reason for prescription).
 20. Subject is being treated with furosemide, hydrochlorothiazide, vigabatrin, vitamin B₆ therapy for epilepsy, monoamine oxidase (A or B) inhibitors, felbamate, zonisamide, or any other medication that is a potent carbonic anhydrase inhibitor (eg, acetazolamide). Past treatment with furosemide for more than 2 weeks must be discussed with the sponsor and the discussion documented.

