7.10. Clinical Laboratory Tests

Figures of the mean change from screening (+/- Standard Error) values in continuous hematology, urinalysis and serum chemistry laboratory parameters will be presented by visit. The observed and change from baseline values of lab parameters will also be summarized by visit. For calculation, the signs “<” or “>” will be removed and resulting numerical value will be used. The reference ranges for labs from the SAP will be used, not the reference ranges provided from the Covance.

The shift table of pre- vs. post-treatment with classes for below, within, and above normal ranges will be presented.

The number and percentage of subjects with markedly abnormal (low, high) laboratory hematology, urinalysis/24-hour urine and serum chemistry parameters during the study (from treatment start to 30 days after last dose or the end of treatment visit date, whichever is later) that were not present at baseline will be provided. [Appendix 2](#) presents the markedly abnormal criteria. The conversion factors for 25 Vitamin D, 1, 25 Vitamin D and PTH are also listed.

The laboratory data will be listed. The subjects with any laboratory results outside the reference ranges and the subjects with any markedly abnormal laboratory results will be listed.

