25 Vitamin D (ng/ml)	<20	>55
1, 25 D (pg/ml)	<15	>90
IGF-1 (nmol/L)	2-8: <6	>50
	9-10: <8	>65
	11-12: <15	>100
	13-16: <20	>140
PTH (pg/mL)	2-7: <40	>350
	8-10: <50	>490
	11-12: <70	>750
	13-16: <100	>1100

The conversion factors for 25 Vitamin D, 1, 25 Vitamin D and PTH are listed below.

Parameter	Units	Conversion factor
25 Vitamin D	nmol/L to ng/mL	0.4
1, 25 Vitamin D	Pmol/L to pg/ml	1.355
PTH	Pmol/L to pg/mL	9.434

Hematology

Laboratory Value (SI Unit)	Lower Limit of Normal (LLN) Range	Upper Limit of Normal (ULN) Range	DNP Recommended Markedly Abnormal: Low	DNP Recommended Markedly Abnormal: High
Hemoglobin (g/L)	Females: 1-4 years: 109 5-10 years: 119 11-17 years: 119 ≥18 years: 119 Males: 1-4 years: 109 5-10 years: 119 11-17 years: 127 ≥18 years: 132	Females: 1-4 years: 150 5-10 years: 150 11-17 years: 150 ≥18 years: 155 Males: 1-4 years: 150 5-10 years: 150 11-17 years: 170 ≥18 years: 177	≤ 90	≥ 180

Hematocrit (proportion of 1.0)	Females: 1-4 years: 0.31 5-10 years: 0.35 11-17 years: 0.34 ≥18 years: 0.35 Males: 1-4 years: 0.31 5-10 years: 0.35 11-17 years: 0.37 ≥18 years: 0.40	Females: 1-4 years: 0.44 5-10 years: 0.44 11-17 years: 0.44 ≥18 years: 0.47 Males: 1-4 years: 0.44 5-10 years: 0.44 11-17 years: 0.48 ≥18 years: 0.52	≤0.85 X LLN	≥1.15 X ULN
RBC – Total (10E12/L)	Females: 1-4 years: 3.8 5-10 years: 4.1 11-17 years: 3.9 ≥18 years: 4.2 Males: 1-4 years: 3.8 5-10 years: 4.3 11-17 years: 4.3 ≥18 years: 4.5	Females: 1-4 years: 5.2 5-10 years: 5.2 11-17 years: 5.1 ≥18 years: 5.4 Males: 1-4 years: 5.5 5-10 years: 5.2 11-17 years: 5.6 ≥18 years: 6.2	≤0.85 X LLN	≥1.15 X ULN

WBC – Total (10E9/L)	2-5 years: 5 6-17 years: 4.5 ≥18 years: 4.5	2-5 years: 15.5 6-17 years: 13.5 ≥18 years: 11	< 0.85 X LLN	> 1.15 X ULN
Neutrophils– WBCDifferential Count(Proportion of 1)	0.38	0.80	≤ 0.15	≥ 0.90
Lymphocytes– WBCDifferential Count(Proportion of 1)	0.15	0.40	≤ 0.10	≥ 0.60
Monocytes– WBCDifferential Count(Proportion of 1)	0	0.13	NA	≥ 0.20

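### SAP Appendix 2 has no absolute neutrophil count, so a count of roughly 574–999/µL can escape both the neutrophil and the white-cell low flags

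*SAP*

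**What the plan says.** SAP 7.10 plans a table by threshold: "The number and percentage of subjects with markedly abnormal (low, high) laboratory hematology", with urinalysis and chemistry alongside, for abnormalities not present at baseline. The criteria come from Appendix 2, and SAP reference ranges replace the central laboratory's.

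In the haematology part of Appendix 2 the neutrophil row reads "Neutrophils– WBCDifferential Count(Proportion of 1", with a normal range of 0.38 to 0.80 and a markedly-low limit of 0.15 or less. Total WBC is markedly low below 0.85 × LLN, and the lower limits are "2-5 years: 5 6-17 years: 4.5" (× 10⁹/L). No row gives an absolute neutrophil count.

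The protocol does use an absolute count. Exclusion criterion 17 in Section 4.2 lists WBC below 3,000/µL "or absolute neutrophil count" below 1,000/µL among clinically significant abnormalities at screening. Protocol 1.1 reports, for children on levetiracetam, small but statistically significant "decreases in white blood cell (WBC) and neutrophil counts and increases in lymphocyte counts, as compared with placebo". It also says that "there was no apparent difference between treatment groups with respect to neutrophil count" when clinically significant low values were compared. Its list of post-marketing reports includes "hepatic failure, hepatitis, leukopenia, neutropenia, pancreatitis, pancytopenia".

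**The concern.** A share of white cells and an absolute count answer different questions. The same 15% is a low count in a child with few white cells and an unremarkable one in a child with many. A threshold on the share and a separate threshold on WBC leave a region where both look acceptable but their product is below the only neutrophil limit in either document.

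At stake is how one haematological safety signal is displayed. The markedly-abnormal table is where a reader would look for a between-arm count of children who became neutropenic on treatment, and it cannot supply one. Overall safety is a study objective, and neutropenia has been reported with the comparator.

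**Working it through.** Inputs (SAP Appendix 2 unless stated):

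- WBC lower limit of normal: 5.0 (ages 2–5) and 4.5 (ages 6–17), × 10⁹/L.
- WBC markedly low: below 0.85 × LLN.
- Neutrophil proportion: markedly low at ≤0.15; lower limit of normal 0.38.
- Other markedly-high limits: lymphocytes ≥0.60, monocytes ≥0.20, eosinophils ≥0.10, basophils ≥0.06.
- Upper limits of normal: monocytes 0.13, eosinophils 0.08, basophils 0.02.
- ANC limit: 1.0 × 10⁹/L (Protocol 4.2, exclusion 17).

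Formula: ANC = WBC × neutrophil proportion. The plan gives no figure of its own to reproduce.

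**Step 1: the gap between the two low flags.** The WBC flag starts below 0.85 × 5.0 = 4.25 and 0.85 × 4.5 = 3.825. The lowest ANC that passes both flags is just above:

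- ages 2–5: 4.25 × 0.15 = 0.638, i.e. 638/µL;
- ages 6–17: 3.825 × 0.15 = 0.574, i.e. 574/µL.

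The gap closes at WBC = 1.0 / 0.15 = 6.67. Inside it the proportion lies above 0.15 and below 1/WBC, so at most 1/4.25 = 0.235 or 1/3.825 = 0.261. Example: 4.5 × 0.20 = 0.900, or 900/µL, with neither flag raised.

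**Step 2: allow for the other differential rows.** If monocytes, eosinophils and basophils are within SAP normal limits, they sum to at most 0.13 + 0.08 + 0.02 = 0.23. Lymphocytes must be below 0.60 to avoid their own flag. Escaping every row then needs neutrophils above 1 − 0.23 − 0.60 = 0.17, so:

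- ages 2–5: ANC above 4.25 × 0.17 = 0.722, i.e. 722/µL;
- ages 6–17: ANC above 3.825 × 0.17 = 0.650, i.e. 650/µL;
- WBC ceiling: 1.0 / 0.17 = 5.88.

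A differential that does this at WBC 4.5: neutrophils 0.20, lymphocytes 0.58, monocytes 0.13, eosinophils 0.07, basophils 0.02 (sum 1.00). ANC is 900/µL and no markedly-abnormal row is met. With lymphocytes at 0.70 instead, the lymphocyte row would be met, but nothing would label the child as having a low neutrophil count.

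**Step 3: the other outputs.** An ANC below 1.0 with a proportion of 0.38 or more needs WBC below 1.0 / 0.38 = 2.63, which the WBC row flags. So every child in the gap has a proportion below 0.38 and is classed as below normal in the shift table and the out-of-range listing. That class is broad: WBC 10 with 30% neutrophils (10 × 0.30 = 3.0, or 3,000/µL) falls in it too.

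**Step 4: the opposite direction.** WBC 15 with 15% neutrophils gives 15 × 0.15 = 2.25, or 2,250/µL, and meets the markedly-low neutrophil row.

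**The case against.** The case for leaving the plan alone is substantial, and most of it stands.

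- A reader might infer that such a child goes unreported. That is wrong. The child is below normal in the shift table and the out-of-range listing, and all laboratory data are listed. Many would also meet the lymphocyte row. Protocol 9.3 requires clinically relevant laboratory changes to be recorded as adverse events, and those are tabulated by arm.
- A reader might infer that the SAP departs from the protocol's definition of neutropenia. There is no such definition: 1,000/µL is an entry criterion. Appendix 2 does not generally carry entry limits over. Vitamin D is <12 ng/mL at entry and <20 in Appendix 2, ammonia ≥2 × and ≥1.5 × ULN, bicarbonate <20 and <17. For total WBC the SAP flag (below 4.25 or 3.825) is more sensitive than the entry limit (below 3.0).
- A reader might infer that a known levetiracetam effect will be misreported. Protocol 1.1 calls the decreases small, reports no apparent group difference in neutrophil count, and says no child discontinued for low counts. Its threshold signal is low total WBC (3.0% versus 0%), which Appendix 2 does flag.
- The proportion row is labelled as a proportion. A child with WBC 15 and 15% neutrophils is correctly shown as having a low share, and nothing calls that child neutropenic.

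What remains is narrower. None of these outputs gives a between-arm count of low ANC. The shift class mixes 900/µL with 3,000/µL. Adverse-event recording depends on the investigator's judgement, and neutropenia and leukopenia are not in the Appendix 3 list of events of clinical interest.

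**Conclusion.** The point holds as a minor gap in one safety table. An ANC of about 574–999/µL (ages 6–17) or 638–999/µL (ages 2–5) can pass both the neutrophil and the WBC markedly-low flags. With the other cell types within SAP limits, passing every differential row as well needs an ANC above about 650 or 722/µL. Lower counts always meet the neutrophil or the WBC row.

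This rests on reading Appendix 2 as the complete list of criteria, as SAP 7.10 indicates, and on using 1,000/µL only as a convenient reporting line. Neither document says how often children fall in this band, so no effect on the arm comparison can be claimed. The documents do not support saying that low counts go unseen, that a protocol definition is breached, or that the comparator's risk will be misstated. They support saying that the plan has no by-arm count of low ANC and could easily have one.

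**What to change.** In SAP Appendix 2 and Section 7.10:

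1. Keep the existing proportion row. Its column is headed as DNP-recommended, and nothing here justifies dropping it.
2. Derive ANC = total WBC × neutrophil proportion at every visit with haematology (screening and Months 1, 3, 6, 9 and 12).
3. Add an ANC row to the markedly-abnormal table at <1,000/µL, labelled as a reporting threshold taken from exclusion criterion 17. It implies no clinical action.
4. Summarise observed ANC and change from baseline by visit and arm.

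Protocol 9.3 already collects WBC with differential, so no new samples or visits are needed. The cost is one derived variable and a few extra table rows.

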11. URINALYSIS

Laboratory Value (SI Unit)	Lower Limit of Normal (LLN) Range	Upper Limit of Normal (ULN) Range	Markedly Abnormal: Low	Markedly Abnormal: High
PH	4.5	8	≤ 4	≥ 8
Specific Gravity	1.007	1.03	≤ 1.001	≥ 1.035

Appendix 3: AE of clinical interest

AETERM	AEBODSYS in MedDRA 22.0	AEDECOD (PT) In MedDRA 22.1
5' nucleotidase increased	Investigations	5' nucleotidase increased
Abulia	Psychiatric disorders	Abulia
Accommodation disorder	Eye disorders	Accommodation disorder
Acidosis	Metabolism and nutrition disorders	Acidosis
Acidosis hyperchloraemic	Metabolism and nutrition disorders	Acidosis hyperchloraemic
Acquired epidermolysis bullosa	Skin and subcutaneous tissue disorders	Acquired epidermolysis bullosa
Acquired pigmented retinopathy	Injury, poisoning and procedural complications	Acquired pigmented retinopathy
Activation syndrome	Psychiatric disorders	Activation syndrome
Acute generalised exanthematous pustulosis	Skin and subcutaneous tissue disorders	Acute generalised exanthematous pustulosis
Acute hepatic failure	Hepatobiliary disorders	Acute hepatic failure
Renal failure acute	Renal and urinary disorders	Acute kidney injury
Adjustment disorder with anxiety	Psychiatric disorders	Adjustment disorder with anxiety
Adjustment disorder with depressed mood	Psychiatric disorders	Adjustment disorder with depressed mood
Adjustment disorder with mixed anxiety and depressed mood	Psychiatric disorders	Adjustment disorder with mixed anxiety and depressed mood
Adjustment disorder with mixed anxiety and depressed mood	Psychiatric disorders	Adjustment disorder with mixed anxiety and depressed mood
Affect lability	Psychiatric disorders	Affect lability
Agitated depression	Psychiatric disorders	Agitated depression
Agitation	Psychiatric disorders	Agitation
Alanine aminotransferase abnormal	Investigations	Alanine aminotransferase abnormal
Alanine aminotransferase increased	Investigations	Alanine aminotransferase increased
Albumin urine present	Investigations	Albumin urine present
Alpha 1 foetoprotein abnormal	Investigations	Alpha 1 foetoprotein abnormal
Alpha 1 foetoprotein increased	Investigations	Alpha 1 foetoprotein increased

Alpha 1 globulin increased	Investigations	Alpha 1 globulin increased
Alpha 2 globulin increased	Investigations	Alpha 2 globulin increased
Alpha globulin increased	Investigations	Alpha globulin increased
Alpha-2 macroglobulin increased	Investigations	Alpha-2 macroglobulin increased
Altered state of consciousness	Nervous system disorders	Altered state of consciousness
Altered visual depth perception	Eye disorders	Altered visual depth perception
Amaurosis	Eye disorders	Amaurosis
Amaurosis fugax	Eye disorders	Amaurosis fugax
Ammonia abnormal	Investigations	Ammonia abnormal
Ammonia abnormal	Investigations	Ammonia abnormal
Ammonia increased	Investigations	Ammonia increased
Ammonia increased	Investigations	Ammonia increased
Amnesia	Nervous system disorders	Amnesia
Global amnesia	Nervous system disorders	Amnesia
Angle closure glaucoma	Eye disorders	Angle closure glaucoma
Anhedonia	Psychiatric disorders	Anhedonia
Anhidrosis	Skin and subcutaneous tissue disorders	Anhidrosis
Anorexia and bulimia syndrome	Psychiatric disorders	Anorexia and bulimia syndrome
Anorexia and bulimia syndrome	Psychiatric disorders	Anorexia and bulimia syndrome
Anorexia nervosa	Psychiatric disorders	Anorexia nervosa
Anorexia nervosa	Psychiatric disorders	Anorexia nervosa
Anterograde amnesia	Nervous system disorders	Anterograde amnesia
Anticipatory anxiety	Psychiatric disorders	Anticipatory anxiety
Antidepressant therapy	Surgical and medical procedures	Antidepressant therapy
Antimetropia	Eye disorders	Antimetropia
Anxiety	Psychiatric disorders	Anxiety
Anxiety disorder	Psychiatric disorders	Anxiety disorder
Apathy	Psychiatric disorders	Apathy
Dysphasia	Nervous system disorders	Aphasia
Aphonia psychogenic	Nervous system disorders	Aphonia psychogenic
Apocrine miliaria	Skin and subcutaneous tissue disorders	Apocrine miliaria

Apraxia	Nervous system disorders	Apraxia
Ascites	Gastrointestinal disorders	Ascites
Aspartate aminotransferase abnormal	Investigations	Aspartate aminotransferase abnormal
Aspartate aminotransferase increased	Investigations	Aspartate aminotransferase increased
Asterixis	Nervous system disorders	Asterixis
Asterixis	Nervous system disorders	Asterixis
Asthenia	General disorders and administration site conditions	Asthenia
Astigmatism	Eye disorders	Astigmatism
Attention deficit/hyperactivity disorder	Psychiatric disorders	Attention deficit/hyperactivity disorder
Atypical attention deficit syndrome	Psychiatric disorders	Atypical attention deficit syndrome
Autoimmune hepatitis	Hepatobiliary disorders	Autoimmune hepatitis
Beta 2 microglobulin increased	Investigations	Beta 2 microglobulin increased
Beta globulin increased	Investigations	Beta globulin increased
Bile duct obstruction	Hepatobiliary disorders	Bile duct obstruction
Bile duct pressure increased	Investigations	Bile duct pressure increased
Bile duct stenosis	Hepatobiliary disorders	Bile duct stenosis
Bile duct stent insertion	Surgical and medical procedures	Bile duct stent insertion
Bile output abnormal	Investigations	Bile output abnormal
Bile output decreased	Investigations	Bile output decreased
Biliary cirrhosis	Hepatobiliary disorders	Biliary cirrhosis
Biliary dyskinesia	Hepatobiliary disorders	Biliary dyskinesia
Biliary fibrosis	Hepatobiliary disorders	Biliary fibrosis
Bilirubin conjugated abnormal	Investigations	Bilirubin conjugated abnormal
Bilirubin conjugated increased	Investigations	Bilirubin conjugated increased
Bilirubin excretion disorder	Hepatobiliary disorders	Bilirubin excretion disorder
Bilirubinuria	Renal and urinary disorders	Bilirubinuria
Biopsy liver abnormal	Investigations	Biopsy liver abnormal

Blepharospasm	Eye disorders	Blepharospasm
Blindness	Eye disorders	Blindness
Blindness cortical	Eye disorders	Blindness cortical
Blindness day	Eye disorders	Blindness day
Blindness transient	Eye disorders	Blindness transient
Blindness traumatic	Injury, poisoning and procedural complications	Blindness traumatic
Blindness unilateral	Eye disorders	Blindness unilateral
Blister	Skin and subcutaneous tissue disorders	Blister
Blood alkaline phosphatase abnormal	Investigations	Blood alkaline phosphatase abnormal
Blood alkaline phosphatase increased	Investigations	Blood alkaline phosphatase increased
Blood bicarbonate abnormal	Investigations	Blood bicarbonate abnormal
Blood bicarbonate decreased	Investigations	Blood bicarbonate decreased
Blood bilirubin abnormal	Investigations	Blood bilirubin abnormal
Blood bilirubin increased	Investigations	Blood bilirubin increased
Blood bilirubin unconjugated increased	Investigations	Blood bilirubin unconjugated increased
Blood cholinesterase abnormal	Investigations	Blood cholinesterase abnormal
Blood cholinesterase decreased	Investigations	Blood cholinesterase decreased
Blood urine	Investigations	Blood urine
Blood urine present	Investigations	Blood urine present
Blunted affect	Psychiatric disorders	Blunted affect
Body height abnormal	Investigations	Body height abnormal
Body height below normal	Investigations	Body height below normal
Body height decreased	Investigations	Body height decreased
Body mass index decreased	Investigations	Body mass index decreased
Body temperature decreased	Investigations	Body temperature decreased
Body temperature increased	Investigations	Body temperature increased
Bone development abnormal	Musculoskeletal and connective tissue disorders	Bone development abnormal
Bone development abnormal	Musculoskeletal and connective tissue disorders	Bone development abnormal
Bone disorder	Musculoskeletal and connective tissue disorders	Bone disorder
Bone disorder	Musculoskeletal and connective tissue disorders	Bone disorder

Bone formation decreased	Musculoskeletal and connective tissue disorders	Bone formation decreased
Bone metabolism disorder	Musculoskeletal and connective tissue disorders	Bone metabolism disorder
Bone pain	Musculoskeletal and connective tissue disorders	Bone pain
Borderline glaucoma	Eye disorders	Borderline glaucoma
Borderline mental impairment	Nervous system disorders	Borderline mental impairment
Bradyphrenia	Psychiatric disorders	Bradyphrenia
Bromosulphthalein test abnormal	Investigations	Bromosulphthalein test abnormal
Budd-Chiari syndrome	Hepatobiliary disorders	Budd-Chiari syndrome
Cachexia	Metabolism and nutrition disorders	Cachexia
Calculus bladder	Renal and urinary disorders	Calculus bladder
Calculus bladder	Renal and urinary disorders	Calculus bladder
Calculus prostatic	Reproductive system and breast disorders	Calculus prostatic
Calculus prostatic	Reproductive system and breast disorders	Calculus prostatic
Calculus ureteric	Renal and urinary disorders	Ureterolithiasis
Calculus urethral	Renal and urinary disorders	Calculus urethral
Calculus urinary	Renal and urinary disorders	Calculus urinary
Carbon dioxide decreased	Investigations	Carbon dioxide decreased
Cardiac arrest	Cardiac disorders	Cardiac arrest
Cardiac death	General disorders and administration site conditions	Cardiac death
Cardiac failure	Cardiac disorders	Cardiac failure
Cardiac failure acute	Cardiac disorders	Cardiac failure acute
Cardiac failure chronic	Cardiac disorders	Cardiac failure chronic
Cardiac failure congestive	Cardiac disorders	Cardiac failure congestive
Cardiac output decreased	Investigations	Cardiac output decreased
Cardiac ventriculogram abnormal	Investigations	Cardiac ventriculogram abnormal

Cardiac ventriculogram left abnormal	Investigations	Cardiac ventriculogram left abnormal
Cells in urine	Investigations	Cells in urine
Change in sustained attention	Psychiatric disorders	Change in sustained attention
Charles Bonnet syndrome	Eye disorders	Charles Bonnet syndrome
Childhood disintegrative disorder	Psychiatric disorders	Child-Pugh-Turcotte score increased
Child-Pugh-Turcotte score increased	Investigations	
Chills	General disorders and administration site conditions	Chills
Chloropsia	Eye disorders	Chloropsia
Cholaemia	Hepatobiliary disorders	Cholaemia
Cholelithiasis	Hepatobiliary disorders	Cholelithiasis
Cholelithiasis obstructive	Hepatobiliary disorders	Cholelithiasis obstructive
Cholelithotomy	Surgical and medical procedures	Cholelithotomy
Cholestasis	Hepatobiliary disorders	Cholestasis
Cholestatic liver injury	Hepatobiliary disorders	Cholestatic liver injury
Cholestatic liver injury	Hepatobiliary disorders	Cholestatic liver injury
Cholestatic pruritus	Skin and subcutaneous tissue disorders	Cholestatic pruritus
Chorioretinitis	Infections and infestations	Chorioretinitis
Choroid tubercles	Infections and infestations	Choroid tubercles
Choroiditis	Eye disorders	Choroiditis
Urine colour abnormal	Renal and urinary disorders	Chromaturia
Chronic fatigue syndrome	General disorders and administration site conditions	Chronic fatigue syndrome
Chronic hepatic failure	Hepatobiliary disorders	Chronic hepatic failure
Chronic hepatitis	Hepatobiliary disorders	Chronic hepatitis
Ciliary muscle spasm	Eye disorders	Ciliary muscle spasm
Circumstantiality	Psychiatric disorders	Circumstantiality

Clang associations	Psychiatric disorders	Clang associations
Cognitive disorder	Nervous system disorders	Cognitive disorder
Cold sweat	Skin and subcutaneous tissue disorders	Cold sweat
Coma	Nervous system disorders	Coma
Coma hepatic	Nervous system disorders	Coma hepatic
Communication disorder	Psychiatric disorders	Communication disorder
Completed suicide	Psychiatric disorders	Completed suicide
Confabulation	Psychiatric disorders	Confabulation
Confusional arousal	Psychiatric disorders	Confusional arousal
Confusional state	Psychiatric disorders	Confusional state
Confusional state	Psychiatric disorders	Confusional state
Conjunctival ulcer	Eye disorders	Conjunctival ulcer
Conjunctivitis	Infections and infestations	Conjunctivitis
Consciousness fluctuating	Nervous system disorders	Consciousness fluctuating
Constricted affect	Psychiatric disorders	Constricted affect
Coprolalia	Psychiatric disorders	Coprolalia
Corneal deposits	Eye disorders	Corneal deposits
Corneal exfoliation	Eye disorders	Corneal exfoliation
Corneal oedema	Eye disorders	Corneal oedema
Corneal opacity	Eye disorders	Corneal opacity
Corneal perforation	Eye disorders	Corneal perforation
Creatine urine abnormal	Investigations	Creatine urine abnormal
Creatine urine decreased	Investigations	Creatine urine decreased
Creatine urine increased	Investigations	Creatine urine increased
Creatinine urine decreased	Investigations	Creatinine urine decreased
Creatinine urine increased	Investigations	Creatinine urine increased
Crocodile tears syndrome	Nervous system disorders	Crocodile tears syndrome
Crying	General disorders and administration site conditions	Crying
Cryptogenic cirrhosis	Hepatobiliary disorders	Cryptogenic cirrhosis
Crystal urine	Investigations	Crystal urine
Crystal urine present	Investigations	Crystal urine present
Cyanopsia	Eye disorders	Cyanopsia
Cycloplegia	Eye disorders	Cycloplegia
Cysteine urine present	Investigations	Cysteine urine present
Cystine urine present	Investigations	Cystine urine present

Daydreaming	Psychiatric disorders	Daydreaming
Deaf mutism	Congenital, familial and genetic disorders	Deaf mutism
Decreased activity	General disorders and administration site conditions	Decreased activity
Anorexia	Metabolism and nutrition disorders	Decreased appetite
Anorexia	Metabolism and nutrition disorders	Decreased appetite
Decreased interest	Psychiatric disorders	Decreased interest
Dehydration	Metabolism and nutrition disorders	Dehydration
Delirium	Psychiatric disorders	Delirium
Depressed level of consciousness	Nervous system disorders	Depressed level of consciousness
Depressed mood	Psychiatric disorders	Depressed mood
Depression	Psychiatric disorders	Depression
Depression postoperative	Injury, poisoning and procedural complications	Depression postoperative
Depression suicidal	Psychiatric disorders	Depression suicidal
Depressive symptom	Psychiatric disorders	Depressive symptom
Derailment	Psychiatric disorders	Derailment
Dermatitis bullous	Skin and subcutaneous tissue disorders	Dermatitis bullous
Dermatitis exfoliative	Skin and subcutaneous tissue disorders	Dermatitis exfoliative
Dermatitis exfoliative generalised	Skin and subcutaneous tissue disorders	Dermatitis exfoliative generalised
Detachment of retinal pigment epithelium	Eye disorders	Detachment of retinal pigment epithelium
Developmental coordination disorder	Nervous system disorders	Developmental coordination disorder
Developmental delay	General disorders and administration site conditions	Developmental delay
Diplopia	Eye disorders	Diplopia
Disorientation	Psychiatric disorders	Disorientation
Disorientation	Psychiatric disorders	Disorientation
Dissociative amnesia	Psychiatric disorders	Dissociative amnesia
Distractibility	Psychiatric disorders	Distractibility

Disturbance in attention	Nervous system disorders	Disturbance in attention
Disturbance in attention	Nervous system disorders	Disturbance in attention
Drug eruption	Skin and subcutaneous tissue disorders	Drug eruption
Drug rash with eosinophilia and systemic symptoms	Skin and subcutaneous tissue disorders	Drug reaction with eosinophilia and systemic symptoms
Dry eye	Eye disorders	Dry eye
Keratoconjunctivitis sicca	Eye disorders	Dry eye
Keratoconjunctivitis sicca	Eye disorders	Dry eye
Dry skin	Skin and subcutaneous tissue disorders	Dry skin
Duodenal varices	Gastrointestinal disorders	Duodenal varices
Dwarfism	Musculoskeletal and connective tissue disorders	Dwarfism
Dysarthria	Nervous system disorders	Dysarthria
Dysgraphia	Nervous system disorders	Dysgraphia
Dyshidrosis	Skin and subcutaneous tissue disorders	Dyshidrotic eczema
Dyshidrosis	Skin and subcutaneous tissue disorders	Dyshidrotic eczema
Dyslalia	Nervous system disorders	Dyslalia
Dysmetropsia	Eye disorders	Dysmetropsia
Dysphemia	Psychiatric disorders	Dysphemia
Dysphonia	Respiratory, thoracic and mediastinal disorders	Dysphonia
Dysphonia psychogenic	Nervous system disorders	Dysphonia psychogenic
Dysphoria	Psychiatric disorders	Dysphoria
Dysprosody	Nervous system disorders	Dysprosody
Dyssomnia	Psychiatric disorders	Dyssomnia
Dysthymic disorder	Psychiatric disorders	Persistent depressive disorder
Echolalia	Psychiatric disorders	Echolalia

Electric shock	Injury, poisoning and procedural complications	Electric shock
Electroconvulsive therapy	Surgical and medical procedures	Electroconvulsive therapy
Electroencephalogram abnormal	Investigations	Electroencephalogram abnormal
Emotional distress	Psychiatric disorders	Emotional distress
Encephalopathy	Nervous system disorders	Encephalopathy
Epidermal necrosis	Skin and subcutaneous tissue disorders	Epidermal necrosis
Epidermolysis	Congenital, familial and genetic disorders	Epidermolysis
Epidermolysis bullosa	Congenital, familial and genetic disorders	Epidermolysis bullosa
Epiphyses delayed fusion	Musculoskeletal and connective tissue disorders	Epiphyses delayed fusion
Erythema multiforme	Skin and subcutaneous tissue disorders	Erythema multiforme
Erythroptosis	Eye disorders	Erythroptosis
Excessive eye blinking	Eye disorders	Excessive eye blinking
Exfoliative rash	Skin and subcutaneous tissue disorders	Exfoliative rash
Eye disorder	Eye disorders	Eye disorder
Eye pain	Eye disorders	Eye pain
Eyelid function disorder	Eye disorders	Eyelid function disorder
Eyelid ptosis	Eye disorders	Eyelid ptosis
Eyelid retraction	Eye disorders	Eyelid retraction
Failure to thrive	Metabolism and nutrition disorders	Failure to thrive
Fanconi syndrome	Congenital, familial and genetic disorders	Fanconi syndrome
Fanconi syndrome acquired	Renal and urinary disorders	Fanconi syndrome acquired
Fanconi syndrome acquired	Renal and urinary disorders	Fanconi syndrome acquired
Fatigue	General disorders and administration site conditions	Fatigue

Feeling cold	General disorders and administration site conditions	Feeling cold
Feeling drunk	General disorders and administration site conditions	Feeling drunk
Feeling guilty	Psychiatric disorders	Feeling guilty
Feeling hot	General disorders and administration site conditions	Feeling hot
Feeling of body temperature change	General disorders and administration site conditions	Feeling of body temperature change
Feeling of despair	Psychiatric disorders	Feeling of despair
Feelings of worthlessness	Psychiatric disorders	Feelings of worthlessness
Flight of ideas	Psychiatric disorders	Flight of ideas
Floppy iris syndrome	Injury, poisoning and procedural complications	Floppy iris syndrome
Flushing	Vascular disorders	Flushing
Folliculitis	Infections and infestations	Folliculitis
Fracture delayed union	Musculoskeletal and connective tissue disorders	Fracture delayed union
Fracture malunion	Musculoskeletal and connective tissue disorders	Fracture malunion
Fracture nonunion	Musculoskeletal and connective tissue disorders	Fracture nonunion
Fundoscopy	Investigations	Fundoscopy
Fundoscopy abnormal	Investigations	Fundoscopy abnormal
Galactose elimination capacity test abnormal	Investigations	Galactose elimination capacity test abnormal
Galactose elimination capacity test decreased	Investigations	Galactose elimination capacity test decreased
Gallbladder cholesterolosis	Hepatobiliary disorders	Gallbladder cholesterolosis
Gallbladder disorder	Hepatobiliary disorders	Gallbladder disorder
Gallbladder enlargement	Hepatobiliary disorders	Gallbladder enlargement
Gallbladder fistula	Hepatobiliary disorders	Gallbladder fistula

Gallbladder mucocoele	Hepatobiliary disorders	Gallbladder mucocoele
Gallbladder necrosis	Hepatobiliary disorders	Gallbladder necrosis
Gallbladder non-functioning	Hepatobiliary disorders	Gallbladder hypofunction
Gallbladder obstruction	Hepatobiliary disorders	Gallbladder obstruction
Gallbladder oedema	Hepatobiliary disorders	Gallbladder oedema
Gallbladder pain	Hepatobiliary disorders	Biliary colic
Gamma-glutamyltransferase abnormal	Investigations	Gamma-glutamyltransferase abnormal
Gamma-glutamyltransferase increased	Investigations	Gamma-glutamyltransferase increased
Gastric varices	Gastrointestinal disorders	Gastric varices
Generalised anxiety disorder	Psychiatric disorders	Generalised anxiety disorder
Genital ulceration	Reproductive system and breast disorders	Genital ulceration
Gianotti-Crosti syndrome	Infections and infestations	Gianotti-Crosti syndrome
Glare	Eye disorders	Glare
Glaucoma	Eye disorders	Glaucoma
Glaucomatous optic disc atrophy	Eye disorders	Glaucomatous optic disc atrophy
Globulin urine present	Investigations	Globulin urine present
Globulins increased	Investigations	Globulins increased
Glucose urine	Investigations	Glucose urine
Glucose urine present	Investigations	Glucose urine present
Glyceric acid urine increased	Investigations	Glyceric acid urine increased
Gonioscopy	Investigations	Gonioscopy
Gonioscopy abnormal	Investigations	Gonioscopy abnormal
Granulomatous liver disease	Hepatobiliary disorders	Granulomatous liver disease
Growth retardation	Musculoskeletal and connective tissue disorders	Growth retardation
Guanase increased	Investigations	Guanase increased
Haematuria	Renal and urinary disorders	Haematuria
Haemoglobin urine	Investigations	Haemoglobin urine
Haemoglobin urine present	Investigations	Haemoglobin urine present
Haemorrhagic ascites	Gastrointestinal disorders	Haemorrhagic ascites

Haemorrhagic hepatic cyst	Hepatobiliary disorders	Haemorrhagic hepatic cyst
Halo vision	Eye disorders	Halo vision
Heat exhaustion	Injury, poisoning and procedural complications	Heat exhaustion
Heat illness	Injury, poisoning and procedural complications	Heat illness
Heat oedema	Injury, poisoning and procedural complications	Heat oedema
Heat stroke	Injury, poisoning and procedural complications	Heat stroke
Hemianopia	Nervous system disorders	Hemianopia
Hemianopia heteronymous	Nervous system disorders	Hemianopia heteronymous
Hemianopia homonymous	Nervous system disorders	Hemianopia homonymous
Hemiapraxia	Nervous system disorders	Hemiapraxia
Hepaplastin abnormal	Investigations	Hepaplastin abnormal
Hepaplastin decreased	Investigations	Hepaplastin decreased
Hepatic atrophy	Hepatobiliary disorders	Hepatic atrophy
Hepatic calcification	Hepatobiliary disorders	Hepatic calcification
Hepatic cirrhosis	Hepatobiliary disorders	Hepatic cirrhosis
Hepatic congestion	Hepatobiliary disorders	Hepatic congestion
Hepatic encephalopathy	Nervous system disorders	Hepatic encephalopathy
